6.5.2. Criteria and Procedures for Dose Interruptions and Adjustments of Study Drug

Dose interruptions and modifications of INCB086550 may occur for participants during the study treatment period. The short half-life of INCB086550 (8.62 hours after a single 100 mg dose) may improve management options for participants who experience irAEs, unobtainable with immune checkpoint monoclonal antibodies, which possess long half-lives. Management guidelines for AEs requiring dose modifications are described for general hematologic and nonhematologic toxicities that are not thought to be immune-related in [Table 11](#). Decisions regarding dose interruptions of INCB086550 should be made using clinical judgment of the investigator, taking into account the possible relatedness of the AE to the study drug and the participant's underlying condition. Adverse events that have a clear alternative explanation or transient (≤ 72 hours) abnormal laboratory values without associated clinically significant signs or symptoms may be exempt from dose-interruption/discontinuation rules. Participants may resume treatment as per management guidelines if no medical condition or other circumstance exists that, in the opinion of the investigator, would make the participant unsuitable for further treatment and participation in the study. Treatment with INCB086550 may be delayed for up to 28 days to allow for resolution of toxicity. The treating investigator should contact the medical monitor to discuss the case of any participant whose treatment has been interrupted for more than 28 days before restarting treatment with INCB086550.

Dose interruptions are permitted in the case of medical/surgical events or logistical reasons not related to study therapy (eg, elective surgery, unrelated medical events, subject vacation, holidays). Participants should be placed back on study therapy within 4 weeks (ie, 28 days) of the scheduled interruption, unless otherwise discussed with the medical monitor. The reason for interruption should be documented accordingly.

Safety concerns should be discussed with the sponsor immediately upon occurrence or awareness to determine if the participant should continue or discontinue study treatment. Additional unscheduled visits with CBC may be performed.

Table 11: Non-Immune-Related Adverse Events Dose Modification Guidelines

CTCAE Severity	Suggested Modification
Hematological toxicities	

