CTCAE Grade 1 or Grade 2	Continue INCB086550 treatment at the discretion of the investigator.
CTCAE Grade 3	
 Restart when toxicity resolves to baseline or \leq Grade 1. First occurrence: Restart at same dose or reduce dose by 1 dose level at the discretion of the investigator after discussion with the medical monitor. Second occurrence: Restart at reduced dose (if not already).
CTCAE Grade 4	Permanently discontinue study drug or discuss with medical monitor if treatment algorithm for CTCAE Grade 3 events (above) is appropriate.
Nonhematological toxicities	
All Grades	
 For irAEs, follow the guidelines in Table 10. 
Permanently discontinue treatment for:
 
 Any liver function abnormalities that meet the definition of Hy's law. Encephalopathy of any grade.
CTCAE Grade 1 or 2	
Continue treatment and initiate supportive care at the discretion of the investigator EXCEPT:
 
 Permanently discontinue treatment for \geq Grade 2 ocular toxicity.
CTCAE \geq Grade 3	
Permanently discontinue study treatment for any \geq Grade 3 nonhematologic toxicity EXCEPT:
 
 Transient (\leq 72 hours) abnormal laboratory values without associated clinically significant signs or symptoms. Laboratory abnormalities \geq Grade 3 without associated clinically significant signs or symptoms. Nondesquamating rash \geq Grade 3 that resolves within 48 hours with standard treatment. 
Grade 3 rash in the absence of desquamation, without mucosal involvement, and not requiring systemic steroids that resolves to \leq Grade 1 in \leq 14 days.
 
 Grade 3 fatigue $<$ 1 week. Nausea, vomiting, and diarrhea adequately controlled with medical therapy within 48 hours. 
 For \geq Grade 3 events that do not require permanent discontinuation, the following guidelines should be used: 
 Restart when toxicity resolves to baseline or \leq Grade 1. First occurrence: Restart at same dose or reduce dose by 1 dose level at the discretion of the investigator after discussion with the medical monitor. Second occurrence: Restart at reduced dose (if not already). Third occurrence: Permanently discontinue study drug.

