INCB086550 is an inhibitor of the creatinine transporter OCT2 (in vitro IC₅₀ of 2.6 μ M). Creatinine increases observed during treatment with INCB086550 may be due to immune-mediated nephritis, inhibition of the OCT2 transporter, or may be unrelated to drug administration. Work-up should begin early and a nephrology consult considered. Assessment and management of INCB086550 should consider the relative increase in creatinine from baseline, and timing of the increase. Guidelines for continuing or withholding INCB086550 treatment and the timing for repeat chemistry laboratory studies are presented in [Table 12](#).

Table 12: Management and Evaluation of Increased Creatinine

CTCAE v5.0 Grade	Guidance for Restarting INCB086550	Monitoring and/or Supportive Care
Relative increase of 1 CTCAE Grade in Cycle 1 (If baseline was within normal range, a change to Grade 1, or if Grade 1 at baseline, a change to Grade 2).	Continue INCB086550 and recheck chemistry labs in 48 hours. If creatinine is stable and there is no further increase in 48 hours, INCB086550 may be continued and labs checked in 48-72 hours. If creatinine increases within 48 hours, withhold INCB086550 and recheck chemistry labs in 48 hours. INCB086550 treatment may resume when creatinine returns to Grade 1 or baseline.	
 Evaluate for alternative etiologies (eg, IV contrast, fluid status) and recheck labs in 48 hours.
Grade 1 ($> \text{ULN} - 1.5 \times \text{ULN}$)	Continue INCB086550.	
 Evaluate for alternative etiologies (eg, IV contrast, fluid status).
Grade 2 ($> 1.5 \times \text{ULN} - 3.0 \times \text{ULN}$)	If creatinine was Grade 1 at baseline, INCB086550 may be continued and labs checked in 48 hours. If creatinine is stable and there is no further increase in 48 hours, INCB086550 may be continued and labs checked in 48-72 hours. If creatinine increases within 48 hours, withhold INCB086550 and recheck chemistry labs in 48 hours. INCB086550 treatment may resume when creatinine returns to Grade 1 or baseline. If creatinine was within normal range at baseline, withhold INCB086550 until resolution to \leq Grade 1.	
 Consult nephrology. Evaluate for alternative etiologies (eg, IV contrast, fluid status). Administer prednisone 0.5-1 mg/kg or equivalent with appropriate taper.

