Grade 3 ($> 3.0 \times \text{ULN} - 6.0 \times \text{ULN}$), Grade 4 ($> 6.0 \times \text{ULN}$), or persistent Grade 2	Permanently discontinue INCB086550.	
 Consult nephrology. Evaluate for alternative etiologies (eg, IV contrast, fluid status). Administer prednisone 1-2 mg/kg or equivalent with appropriate taper. If elevations persist for > 3 days, consider mycophenolate.

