6.5.3. Criteria for Permanent Discontinuation of Study Drug

The occurrence of unacceptable toxicity not caused by the underlying disease will require that the study drug be permanently discontinued. Unacceptable toxicity is defined as follows:

- The occurrence of an AE that is related to study drug that, in the judgment of the investigator or the sponsor's medical monitor, compromises the participant's ability to continue study-specific procedures or is considered to not be in the participant's best interest.

- Adverse events requiring treatment discontinuation are found in [Table 10](#) and [Table 11](#).
- A persistent AE requiring a delay of therapy for more than 4 weeks (ie, 28 days) unless a greater delay has been approved by the sponsor.

See Section [7](#) for discontinuation procedures.

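### For a symptom-free Grade 3 or 4 creatinine rise not thought to be immune-related, Protocol Table 11 allows restart after recovery, Table 12 requires a permanent stop, and no text says which governs.

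*Protocol*

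**What the plan says.** Four parts of the Protocol bear on a creatinine value above 3.0 x ULN, which is Grade 3 or 4 in Table 12.

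- **Table 11 (Section 6.5.2).** The text limits this table to "general hematologic and nonhematologic toxicities that are not thought to be immune-related". For nonhematologic toxicity of Grade 3 or higher the default is permanent discontinuation, with listed exceptions. One exception is laboratory abnormalities at or above "Grade 3 without associated clinically significant signs or symptoms", with no time limit. Excepted events restart on recovery to baseline or Grade 1 or lower, and the third occurrence is a permanent stop. Immune-related events are sent to Table 10.
- **Table 12 (Section 6.5.2).** The introductory paragraph says that creatinine increases "may be due to immune-mediated nephritis, inhibition of the OCT2 transporter, or may be unrelated to drug administration", and refers the reader to Table 12 for continuing or withholding drug. The row for Grade 3, Grade 4 or persistent Grade 2 reads "Permanently discontinue INCB086550", without exception.
- **Section 6.5.2, opening text.** "Adverse events that have a clear alternative explanation or transient" (72 hours or less) abnormal laboratory values "without associated clinically significant signs or symptoms may be exempt from dose-interruption/discontinuation rules".
- **Pointers.** Table 10 (Section 6.5.1) sends nephritis and raised creatinine to Table 12 and describes it as guidance for immune-related renal events. Section 6.5.3 states: "Adverse events requiring treatment discontinuation are found in" Tables 10 and 11. It does not name Table 12. Section 7.1.1 makes discontinuation mandatory for unacceptable toxicity as defined in Section 6.5.3.

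**The concern.** The two tables overlap for creatinine rises that are not thought to be immune-related, and for symptom-free rises in that group they end differently. Under one, the participant may go back on drug after recovery; under the other, treatment is over.

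The case is foreseeable. The Protocol states a non-immune mechanism for creatinine rises (OCT2 inhibition), and Table 12 names IV contrast as an etiology to check. Section 8.2.1 requires contrast CT or MRI at baseline unless there is an allergy or medical monitor approval, and asks for the same technique throughout.

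At stake is whether an irreversible treatment decision follows from the participant's condition or from which table the site opened. The SAP (Section 9.2.3 and Appendix A, Table 3.2.7) plans a summary of TEAEs leading to discontinuation of study drug, so site-dependent stops would enter a reported safety result. If Table 12 was meant to bind in every case, a restart under Table 11 would depart from an intended safety rule.

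**Working it through.** No alpha, power, sample size or margin enters this point, and the plan gives no figure to reproduce. The check follows a Grade 3 or 4 creatinine value through the rules, split by suspected cause and symptoms.

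| Case | Via Table 11 | Via Table 12 | Result |
|---|---|---|---|
| (a) Symptom-free, not thought immune-related | Laboratory exception applies: restart after recovery, permanent stop at third occurrence | Permanent discontinuation | **Conflict** |
| (b) Symptom-free, thought immune-related | Sent to Table 10, which sends it to Table 12 | Permanent discontinuation | Tables agree |
| (c) With significant symptoms, clear alternative explanation, not immune-related | No exception for explained events; default is permanent discontinuation | Permanent discontinuation | Tables agree |
| (d) Symptom-free, clear alternative explanation, not immune-related | As (a) | As (a) | **Conflict, as (a)** |

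The conflict is therefore confined to symptom-free, non-immune rises. Having an explanation adds nothing at table level.

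**Does any text settle cases (a) and (d)?**

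1. The paragraph before Table 12 gives that table all-cause scope, which favors Table 12.
2. Table 10 describes Table 12 as immune-related guidance, which leaves non-immune events to Table 11.
3. Table 11 does not mention Table 12.
4. Section 6.5.3 names Tables 10 and 11 only. Table 12 is reached from there only through Table 10, that is, by the immune-related route.
5. The opening text of Section 6.5.2 is permissive. Its symptom-free limb is limited to 72 hours, and it does not say whether it reaches Table 12. This is an ambiguity, not a contrary instruction.

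A site that judges a rise non-immune and follows Section 6.5.3 arrives at Table 11. A site that reads the paragraph above Table 12 arrives at a permanent stop. Both follow the written text.

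**Size.** Section 2.2.2 reports increased blood creatinine in 20.8% of 48 Phase 1 participants: 0.208 x 48 = 9.98, about 10. The documents do not give the share at Grade 3 or higher. Assume it is 0 to 10% of those cases:

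- lower end: 20.8% x 0 = 0%
- upper end: 20.8% x 0.10 = 2.08%, about 2.1%

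With the cohort sizes of 23 to 42 in Protocol Table 20, the upper end is 0.0208 x 23 = 0.48 to 0.0208 x 42 = 0.87 participants per cohort. This still includes immune-related and symptomatic rises, where the tables agree, so under the assumption it is an upper limit on those exposed to the conflict.

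**The case against.** The strongest reply is structural. Section 6.5.2 describes Table 11 as covering general toxicities and then gives creatinine its own paragraph and table. A site with a raised creatinine would naturally use that table, and a specific rule usually displaces a general one. This is a plausible reading, but no sentence adopts it, and the Table 10 description and the Section 6.5.3 pointer work against it.

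A second reply is that safeguards exist. Section 6.5 asks investigators to discuss dose modifications with the medical monitor, and Section 6.5.2 asks for safety concerns to be discussed with the sponsor immediately. Section 6.5.1 allows rechallenge, with medical monitor approval, after immune-related events of Grade 3 or higher that require permanent discontinuation under Table 10. The discussions may catch individual cases and reduce variation between sites, but they supply no written rule for a non-immune rise.

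Four stronger readings are tempting, and the documents do not support them.

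- *Every Grade 3 or 4 creatinine rise receives opposite instructions.* Immune-related rises are routed consistently from Table 11 to Table 10 to Table 12.
- *A clearly explained rise is exempt in one place and a mandatory stop in another.* Table 11 has no exception for explained events. That limb rests only on the discretionary sentence in Section 6.5.2, which can be read as a permitted departure from Table 12.
- *Table 11 lets sites dose through a Grade 3 or 4 value.* Its excepted events restart only after recovery. The tables differ on whether drug may be restarted later.
- *ORR depends on which table was used.* This is not shown. Few participants could be affected, those who stop without progression continue to be imaged (Sections 8.2.1.2 and 8.2.1.3), and a confirmed response already reached still counts.

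**Conclusion.** The inconsistency is real and narrow. For a Grade 3 or 4 creatinine rise without clinically significant signs or symptoms and not thought to be immune-related, Tables 11 and 12 give incompatible outcomes on permanent discontinuation, and the Protocol does not say which prevails. This rests on the text alone and needs no numerical assumption.

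The number exposed is small and uncertain: 0 to about 2.1% of participants under the assumed 0 to 10% share at Grade 3 or higher, or fewer than one participant per cohort at the planned sizes. Section 2.2.2 says that most Phase 1 TEAEs were Grade 1 or 2. The practical reach is smaller still, because the SAP (Sections 1 and 11.2.1) records early termination with minimal enrollment. Sample size, power and Type I error are unaffected.

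The passages should nevertheless be reconciled: the decision concerned is irreversible, it feeds a planned safety summary, and the repair is only wording.

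**What to change.** Reconcile five places: the creatinine row of Table 10, the exemption sentence in the opening text of Section 6.5.2, the laboratory exception in Table 11, Table 12 with its introductory paragraph, and the pointer in Section 6.5.3.

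- State whether Table 12 applies to creatinine increases of every cause or only to immune-related ones, and use the same description in Table 10 and in the paragraph before Table 12.
- State which text takes precedence for a symptom-free rise of Grade 3 or higher that is not thought to be immune-related, and put a matching cross-reference in Table 11.
- Say whether the permissive exemption in Section 6.5.2 extends to Table 12.
- Align the list of tables in Section 6.5.3 with the answer.

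Which clinical rule applies is for the sponsor to decide, and none is proposed here. The cost is a few sentences and cross-references at a protocol amendment, or in any later protocol that reuses this text, with no change to the design or analysis. For data already collected, SAP Listing 2.7.4 covers adverse events leading to interruption, reduction or discontinuation, so any participants stopped for raised creatinine can be identified there.

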6.5.3. Criteria for Permanent Discontinuation of Study Drug

The occurrence of unacceptable toxicity not caused by the underlying disease will require that the study drug be permanently discontinued. Unacceptable toxicity is defined as follows:

- The occurrence of an AE that is related to study drug that, in the judgment of the investigator or the sponsor's medical monitor, compromises the participant's ability to continue study-specific procedures or is considered to not be in the participant's best interest.

- Adverse events requiring treatment discontinuation are found in [Table 10](#) and [Table 11](#).
- A persistent AE requiring a delay of therapy for more than 4 weeks (ie, 28 days) unless a greater delay has been approved by the sponsor.

See Section [7](#) for discontinuation procedures.

6.5.4. Treatment After Initial Evidence of Radiologic Evidence of Disease Progression

Immunotherapeutic agents such as INCB086550 may produce antitumor effects by potentiating endogenous cancer-specific immune responses. The response patterns seen with such an approach may extend beyond the typical time course of responses seen with cytotoxic agents and can manifest as a clinical response after an initial increase in tumor burden or even the appearance of new lesions.

If radiologic imaging shows PD, tumor assessment should be repeated \geq 4 weeks later to confirm PD, with the option of continuing treatment as described in the following text while awaiting radiologic confirmation of progression. If repeat imaging shows a reduction in the tumor burden compared with the initial scan demonstrating PD, treatment may be continued according to the treatment calendar. If repeat imaging confirms PD, participants will be discontinued from study treatment. In determining whether the tumor burden has increased or decreased, investigators should consider all target lesions as well as nontarget lesions.

When feasible, participants should not be discontinued until progression is confirmed; however, the decision to continue study treatment after the first evidence of disease progression is at the investigator's discretion based on the clinical status of the participant as described in [Table 13](#).

Participants may receive study treatment while waiting for confirmation of PD if they are clinically stable as defined by the following criteria:

- Absence of signs and symptoms (including worsening of laboratory values) indicating disease progression.
- No decline in ECOG performance status.
- Absence of rapid PD.
- Absence of progressive tumor at critical anatomical sites (eg, cord compression) requiring urgent alternative medical intervention.

Table 13: Imaging and Treatment After First Radiologic Evidence of Progressive Disease

	Clinically Stable		Clinically Unstable	
	Imaging	Treatment	Imaging	Treatment
First radiologic evidence of PD	Repeat imaging at \geq 4 weeks to confirm PD	May continue study treatment at the investigator's discretion while awaiting confirmatory scan	Repeat imaging at \geq 4 weeks to confirm PD if possible	Discontinue treatment
Repeat scan confirms PD	No additional imaging required	Discontinue treatment	No additional imaging required	N/A
Repeat scan shows SD, PR, or CR	Continue regularly scheduled imaging assessments every 8 weeks	Continue study treatment at the investigator's discretion	Continue regularly scheduled imaging assessments every 8 weeks	May restart study treatment if condition has improved and/or is clinically stable per investigator's discretion

6.6. Concomitant Medications and Procedures

All concomitant medications and treatments (including over-the-counter or prescription medicines, vitamins, vaccines, and/or herbal supplements) must be recorded in the eCRF. Any prior medication received up to 28 days before the first dose of study drug and 30 days after the last dose of study drug, or until the participant begins a new anticancer therapy, whichever occurs first, will be recorded in the eCRF. Any addition, deletion, or change in the dose of these medications will also be recorded. Concomitant medications administered more than 30 days after the last dose of study drug should be recorded for SAEs as defined in Section 9.3. Concomitant treatments/procedures that are required to manage a participant's medical condition during the study will also be recorded in the eCRF. The medical monitor should be contacted if there are any questions regarding concomitant or prior therapy.

6.6.1. Permitted Medications and Procedures

All treatments that the investigator considers necessary for a participant's welfare may be administered at the discretion of the investigator, in keeping with the community standards of medical care, except those specifically defined as prohibited (see Section 6.6.3). All concomitant medications will be recorded in the eCRF, including all prescription and over-the-counter medications, herbal supplements, and IV medications and fluids. If changes occur during the study, documentation of drug regimen, frequency, route, and date may also be included in the eCRF.

Use of prophylactic growth factors should be based on ASCO or ESMO guidelines for the use of WBC growth factors (Crawford et al 2010, Smith et al 2015) and the investigator's clinical judgment. Bisphosphonates are allowed while participants are receiving study treatment.

6.6.2. Restricted Medications and Procedures

6.6.2.1. P-glycoprotein Substrates

INCB086550 is an inhibitor of P-gp and BCRP. Concomitant medications that are P-gp substrates with a narrow therapeutic index (eg, apixaban, colchicine, cyclosporine, dabigatran, digoxin, edoxaban, rivaroxaban, and tacrolimus) should be administered with caution and INCB086550 administration should be separated by a least 6 hours before or after the administration of the P-gp substrate.

6.6.2.2. Metformin

INCB086550 is an inhibitor of the creatinine transporter OCT2. Metformin is an OCT2 substrate and should be administered with caution. Careful monitoring of blood glucose levels should be performed when metformin is administered as a concomitant medication.

6.6.2.3. Stomach Acid-Reducing Medications

Since the impact on INCB086550 absorption is unknown, stomach acid-reducing medications such as proton pump inhibitors and H₂-receptor blockers should be used with caution. For participants who have a requirement for stomach acid-reducing medication, H₂-receptor blockers should be considered rather than proton pump inhibitors. H₂-receptor blockers should be administered > 2 hours after INCB086550 administration.

